## PROTOCOL SYNOPSIS

Study Title	Testing Product Messages in Colombia
Funder	Bloomberg Philanthropies
Study Rationale	
According to the WHO, obesity and overweight are health conditions afflicting over a billion people worldwide. Obesity and overweight can lead to numerous health problems including cardiovascular disease, diabetes, musculoskeletal disorders, and various types of cancers (1). Colombia is not immune to this global health problem. In Colombia in 2016, more than half of adults were overweight and more than 22 percent of adults were obese (2). Additionally, obesity and overweight impact Colombian children. The Colombian Ministry of Health reports that approximately 18% of Colombian youth are overweight (3). As a result of this increasing health problem, the Colombian government has begun to take actions to address overweight and obesity in Colombia. The Colombian government (the Congress, the Ministry of Health) recently approved a law that would require warnings on the front of packages high in critical nutrients to inform consumers and reduce the intake of these unhealthy foods and beverages (4). Similar laws have been implemented in countries around the world, such as Chile, Peru, and Israel (5). Research is needed to inform the design of this law. The purpose of this study is to test the potential effectiveness of different labels to be used on the packaging of foods and drinks to promote healthy diets in Colombia. This research is time sensitive and politically relevant and will help to inform Colombian Ministry of Health as to how product labeling will help to dissuade consumption and inform Colombians of product healthfulness prior to the implementation.

Study Objective(s)	
Primary
 

• To identify the impact of nutrient warnings on product selection and other outcomes compared to GDA labels, Nutriscore labels, and a no-label control, in Colombia.

 
Secondary
 

• To determine the effect of the nutrient warning label and the impact of the nutrient warning label on behavioral outcomes.

Study Design	Participants will electronically acknowledge their consent to participate in the study. The study platform (Qualtrics) will randomize participants to one of the four front-of-package label

---

conditions: nutrient warning, Nutri-Score, GDA, or a no-label control. The participants will complete a fruit-drink selection task, inquiring about healthfulness of fruit drinks with each designated front-of-package label. After completing the fruit-drink task, the participant will complete a single product assessment task. After these, the participants will answer objective understanding and perceived message effectiveness questions about a breakfast cereal. Finally, the participants will see one product with all three label types and select the most discouraging label. The study will end with standard demographic questions.

---

Subject Population	Inclusion Criteria
key criteria for Inclusion and Exclusion:	

1. 18 years old or older

2. Currently reside in Colombia

	Exclusion Criteria
	

1. Participated in previous studies linked to this study

Number Of Subjects	Approximately 8,000
Study Duration	Each subject's participation will last approximately 15-20 minutes. The entire study is expected to last 1 month.
Study Phases	

(1) Screening: screening for eligibility and obtaining consent

(2) Randomization: Randomly assigning participants to one of four conditions

(3) Survey: Direct participants to a Qualtrics survey measuring product selection and perceptions and reactions to front-of-package labels, as well as standard demographics.

Statistical Analysis Plan	We will descriptively report unadjusted means (and standard deviations) and percentages for the primary and secondary outcomes. We will use linear regression for continuous outcomes and logistic regression for dichotomous outcomes. We will conduct pairwise comparisons of the predicted means to examine differences by all label types. We will examine whether primary outcomes differ by education.
DATA AND SAFETY MONITORING PLAN	Researchers will store the study data on a remote terminal server, and only research investigators and staff will have access to the data.

---

## BACKGROUND AND RATIONALE

### Introduction

According to the WHO, obesity and overweight are health conditions afflicting over a billion people worldwide. Obesity and overweight can lead to numerous health problems including cardiovascular disease, diabetes, musculoskeletal disorders, and various types of cancers (1). Colombia is not immune to this global health problem. In Colombia in 2016, more than half of adults were overweight and more than 22 percent of adults were obese (2). Additionally, obesity and overweight impact Colombian children. The Colombian Ministry of Health reports that approximately 18% of Colombian youth are overweight (3).

As a result of this increasing health problem, the Colombian government has begun to take actions to address overweight and obesity in Colombia. The Colombian government (the Congress, the Ministry of Health) passed a law in 2021 that would require nutrient warnings on the front of packages high in critical nutrients to inform consumers and reduce the intake of these unhealthy foods and beverages (4). Similar laws have been implemented in countries around the world, such as Chile, Peru, and Israel (5).

Research is needed to inform the design of this law. The purpose of this study is to test the potential effectiveness of different labels to be used on the packaging of foods and drinks to promote healthy diets in Colombia. This research is time sensitive and politically relevant and will help to inform Colombian Ministry of Health as to how product labeling will help to dissuade consumption and inform Colombians of product healthfulness prior to the implementation.

## STUDY OBJECTIVE

The purpose of this study is to determine what type of front-of-package label, whether a Nutri-Score label, nutrient warning label, or a guideline daily amount (GDA) label discourage purchases of “high in” fruit drink products for adult Colombian consumers.

### Primary Outcomes

- Selection of the less healthy fruit drink as the fruit drink the participant would rather buy.
- Correctly identifying which fruit drink was higher in sugar.

### Secondary Outcomes

- Perceived message effectiveness.
- Purchase likelihood of a product in the next week if it were available.
- Percentage of participants that correctly identify the less healthy product when selecting between two products.
- Percentage of participants who correctly identify that the product contains excess sugar, saturated fat, or sodium.
- Percentage of participants selecting each nutrient label as most discouraging them from consuming the product.

## INVESTIGATIONAL PLAN (brief overview)

### Study Design

The study design is a between-subjects randomized controlled trial. Qualtrics will randomly assign participants to one of four study arms in the Qualtrics survey. Participants will have an equal chance of being randomized to any of the trial arms.

#### Study Arms:

1. Control Arm: no warning labels
2. Nutri-Score Label Arm: one label with a color-coded ranking A-E of the relative healthfulness of a product.
3. Nutrient Warning Label: one black, octagonal warning label with the text: "Exceso de [azúcares; grasas saturadas; or /sal/sodio]. Minsalud" followed by the text: "Evitar Su Alto Consumo"
4. Guideline Daily Amount Label Arm: five blue rectangular boxes including calories, total fat, saturated fat, sugar, and sodium given in kcal, g, respectively, and mg for sodium. Followed by the text: "De los valores diarios de referencia de nutrientes en una dieta de 2000 kcal."

In Qualtrics, participants will be asked to complete three tasks. The products presented in each task will have a Nutri-Score label, nutrient label, GDA label, or no labels, depending on which arm the participant has been randomized to.

As the purpose of the study is to inform Colombia's front-of-package labeling policy, we set out to test front-of-package labels that have been implemented in other countries. Potential labeling options were determined through consultation with a food and health advocacy coalition in Colombia, who provided insight on which labels were most likely to be proposed as regulatory options in the Colombian legislature or Ministry of Health. As a result of these conversations, we decided to compare the GDA label (which the food industry has promoted), Nutri-Score label, and a no-label alternative to the nutrient warnings on specific outcomes related to identifying and discouraging selection of ultra-processed foods. We hypothesized that the nutrient warnings would perform best on all outcomes, as previous research has found nutrient warnings to perform best on such outcomes (6).

After completing drink/product selection task, participants will complete a Qualtrics survey measuring reactions to and perceptions of all three labels as well as standard demographics. Upon completion, participants will earn a pre-determined amount of points from Offerwise for completing the study. Participants are able to convert points into money once they accumulate a specified amount.

#### **Study Duration, Enrollment and Number of Subjects**

Participation in the study will last approximately 15-20 minutes. The entire study is expected to last one month.

#### **Study Population**

##### **Inclusion Criteria**

1. 18 years old or older
2. Currently reside in Colombia

##### **Exclusion Criteria**

1. Participation in previous studies linked to this study

## **STUDY PROCEDURES (what will be done)**

#### **Study Steps**

Participants will be recruited through Offerwise, a market research company with over 300,000 panel participants in Colombia. If interested, panel members will complete a screener in Qualtrics to see if they are eligible. If they are not eligible, panel members will be redirected to a termination page indicating they are not eligible to participate. If they are eligible, panel members will be redirected to a consent form. If they agree to the consent form, they will acknowledge their consent by clicking an arrow to proceed to the study.

Following online consent, Qualtrics will equally randomize participants to one of the four front-of-package label conditions: nutrient warning, Nutri-Score, GDA, or a no-label condition. On Qualtrics, participants will complete three tasks. They will be asked to complete a selection task, in which participants will be asked to select which fruit drink is higher in sugar, which they would rather buy, and which is most unhealthy. The fruit drinks will be displayed with the labels corresponding to the participant's randomly assigned label condition. We will only include selection tasks for one type of product due to survey space constraints. Following the selection tasks, the participant will be asked to complete a single product assessment task. They will view a prompt that reads: "The next questions are about food products. You will look at a few different products and answer questions about each one. Please keep in mind that this study seeks to evaluate your survey responses and not the sale of the product." Then, they will answer a series of questions about the yogurt, cookies, and sliced bread, which will show the participant's randomly assigned label condition. The participants will answer all questions about one product at a time (displayed in random order). After these, the participants will answer objective understanding and PME questions about the breakfast cereal. The breakfast cereal is always displayed last as the nutrient warning condition contains two labels. Finally, the participants will be randomly assigned to see the yogurt, cookies, or sliced bread again (one product only). However, this time, the product will not fashion a label. Instead, the three label types (nutrient warnings, GDA, and Nutri-Score) will be displayed underneath the product and the participant will be asked to select the most discouraging label. The study will end with standard demographic questions.

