### **SCREENING AND MONITORING EVALUATIONS AND MEASUREMENTS (how measurements will be made)**

Measurements will include results from the selection and assessment tasks as well as subjective responses by participants. Secondary outcomes will include a variety of measurements, including perceived message effectiveness, 5-point Likert scale questions, and identification questions.

Question	Response Scale
Primary outcomes	
Which of these products would you rather buy?	1 = (image of control beverage) 2 = (image of experimental beverage)
Which of these products is higher in sugar?	1 = (image of control beverage) 2 = (image of experimental beverage)
Secondary outcomes	
How much does this label... 
 
make you concerned about the health consequences of consuming this product?
 
discourage you from wanting to eat consume this product?
 
make consuming this product seem unpleasant to you?
 
	1 = Very much 2 = A lot 3 = A little 4 = Very little 5 = Not at all
How likely is it for you to want to purchase this product next week, if it were available?	1 = Very much 2 = A lot 3 = A little 4 = Very little 5 = Not at all
In your opinion, which of these products is most unhealthy?	1 = (image of control beverage) 2 = (image of experimental beverage)
Do you think this product has excess [saturated fat/sugar/sodium]?	1 = Yes 0 = No
Which of these labels would discourage you most from wanting to consume this product?	[answer choices are each of the label types randomly displayed]

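### Should the protocol fix the order of the fruit-drink questions so that buying is asked before sugar?

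*Combined protocol and SAP*

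**What the plan says.** Study Steps is the only place that describes the fruit-drink questions as a procedure: "participants will be asked to select which fruit drink is higher in sugar, which they would rather buy, and which is most unhealthy". It contains no sequence word for these three items and no statement that they are randomised. The Protocol Synopsis only names the task ("The participants will complete a fruit-drink selection task").

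Three other places put buying ahead of sugar: Primary Outcomes, the measurement table under Screening and Monitoring Evaluations and Measurements, and the primary hypotheses in the SAP.

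Order is specified for some other parts of the survey. Yogurt, cookies and sliced bread appear in random order. For cereal, "The breakfast cereal is always displayed last as the nutrient warning condition contains two labels". For the closing question on the most discouraging label, the table notes that "answer choices are each of the label types randomly displayed".

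Study Steps also says that the selection task uses one product type only and comes before the single-product assessment.

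**The concern.** The Study Objective is to learn which label discourages purchase of the high-sugar drink, so the buying choice matters most for policy. If the survey followed the sequence in Study Steps, each respondent would have just judged the same two drinks on sugar before saying which to buy.

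The arms differ in what a respondent can do with that cue. Under Study Arms, the GDA label is "five blue rectangular boxes including calories, total fat, saturated fat, sugar, and sodium" and the warning names the nutrient in excess. Nutri-Score is "one label with a color-coded ranking A-E of the relative healthfulness of a product", and control carries nothing. A prompt that works through the label could therefore shift the buying contrasts of warning against Nutri-Score and warning against control. Randomisation would not separate a label effect from a prompt-by-label effect. With only one drink pair, no second choice made before a sugar question is available as a check. Asking buying first looks like a free improvement.

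**Working it through.** **1. What the text fixes.** The places that mention the drink questions compare as follows.

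| Place | Sequence given | Nature of the list |
|---|---|---|
| Study Steps | sugar, buying, most unhealthy | content of the task, no sequence word |
| Primary Outcomes | buying, sugar | outcome list |
| Measurement table | buying, sugar; most unhealthy further down, after message effectiveness and purchase likelihood | grouped by primary or secondary status |
| SAP primary hypotheses | buying, sugar | hypothesis list |
| Synopsis | none | names the task |

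None of these is a display order. The orders that the protocol does fix concern products and answer choices. It gives no clear question sequence within any product, including yogurt, cookies, bread and cereal, so the drink task has not been singled out. The Qualtrics questionnaire, where the order would be visible, is not among the documents.

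**2. The plan's own figure.** Sample Size and Power gives f = 0.037 and an odds ratio of 1.14 for about 8,000 participants, alpha 0.05 and 80% power. For a four-group ANOVA, the noncentrality is f² × N = 0.037² × 8,000 = 10.95, which gives power 0.802. Converting, d = 2f = 0.074 and OR = exp(0.074 × π/√3) = 1.144. The figure reproduces as a four-group omnibus calculation. Question order does not enter it, so reordering the items would change neither power nor sample size.

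**3. The yardstick in percentage points.** The rate of choosing the less healthy drink is not given, so 50% and 30% are assumed.
- 50%: odds 1/1.14, rate 0.467, difference 3.3 points.
- 30%: odds 0.4286/1.14, rate 0.273, difference 2.7 points.

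**4. How sensitive a contrast is to a shift.** Assume n = 8,000/4 = 2,000 per arm, no label effect on unprompted choice, and a differential shift d:

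se = √{[p0(1 − p0) + (p0 − d)(1 − p0 + d)]/2,000}

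P(significant) = Φ(d/se − z) + Φ(−d/se − z)

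Here z = 1.960 for alpha 0.05 and z = 2.394 for alpha 0.0167. The second is an assumed Bonferroni correction for three warning contrasts; the SAP promises a correction but names no method.

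| Base rate | Alpha | d = 1 point | d = 2 points | d = 3 points |
|---|---|---|---|---|
| 50% | 0.05 | 0.097 | 0.244 | 0.476 |
| 30% | 0.05 | 0.107 | 0.286 | 0.557 |
| 50% | 0.0167 | 0.040 | 0.130 | 0.310 |
| 30% | 0.0167 | 0.046 | 0.159 | 0.385 |

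These values describe any differential bias of 1 to 3 points in a binary outcome with 2,000 per arm. They contain nothing specific to question order. Applied to the sugar item with the same base rates and shifts, the formula returns the same table, so it cannot show which item should come first.

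**5. The reordering itself.** With buying first, the sugar answer follows a choice between the same two drinks. In the no-label arm, respondents may have to guess which drink has more sugar, and a guess can be drawn towards or away from the drink just chosen. In the labelled arms there is more to go on. That carry-over could also differ by arm, by the same reasoning as the prompt effect. Randomising the two items would balance the exposures, but about 2,000/2 = 1,000 per arm would still answer the buying question after the sugar question.

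**The case for a change.** The strongest case for a change is that the omission falls on the one task that yields both primary outcomes. The mechanism is plausible and depends on arm, the trial is sized for differences of about 3 points, and the remedy costs one sentence and a survey setting. The sugar item has a factual answer, so it may be the sturdier of the two and the better one to place second.

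Part of this stands. The order is not stated, and a reader would want to know it. If sugar did come first, the buying result should be read as a choice made after a sugar question.

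The rest does not carry. The harm needs two conditions, a sugar-first display and a prompt that acts differently by arm, and the documents show neither. The direction is also open: the Nutri-Score grade may itself be read as a sugar cue, and the sign for warning against GDA is unclear. A factual answer protects the sugar item only where respondents can find it, which is least likely in the control arm. The 3-point yardstick is loose as well, because odds ratio 1.14 is an omnibus figure. With 2,000 per arm it gives pairwise power of only about 54% at a 50% base rate and 47% at 30%.

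**Conclusion.** No change to the plan is needed. The protocol leaves the order of the three drink questions unstated, and one sentence happens to list sugar before buying. It does not prescribe asking sugar first.

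Under any common order the four arms remain comparable by randomisation. The order affects the setting in which choice is measured, which is a matter of interpretation and is met by reporting the order used. Buying first, sugar first and a randomised order are all defensible. Each protects one primary outcome at some possible cost to the other, and the documents give no reason to rank them.

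The size of any order effect cannot be derived from the documents. The range of about 10% to 56% for a significant contrast at 0.05 (4% to 39% at 0.0167) rests on assumed shifts of 1 to 3 points, assumed base rates of 30% and 50%, and the assumption of no label effect on unprompted choice. It shows how sensitive a contrast is to a bias of that size, and is no evidence that such a bias occurs.

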#### **Subject Completion/Withdrawal Procedures**

A study participant is determined to have completed the study when they have finished and exited the study survey. To withdraw their data from the study, a participant would have to contact the study team or the university IRB.

#### **Screen Failure Procedures**

Prior to entering into the study, individuals will complete a survey screener. If the individual is younger than 18 years old or does not live in Colombia, they will be deemed ineligible. Such participants will be redirected to a screen notifying them that they are ineligible for the study.

### **SCREENING AND MONITORING EVALUATIONS AND MEASUREMENTS (how measurements will be made)**

Measurements will include results from the selection and assessment tasks as well as subjective responses by participants. Secondary outcomes will include a variety of measurements, including perceived message effectiveness, 5-point Likert scale questions, and identification questions.

Question	Response Scale
Primary outcomes	
Which of these products would you rather buy?	1 = (image of control beverage) 2 = (image of experimental beverage)
Which of these products is higher in sugar?	1 = (image of control beverage) 2 = (image of experimental beverage)
Secondary outcomes	
How much does this label... 
 
make you concerned about the health consequences of consuming this product?
 
discourage you from wanting to eat consume this product?
 
make consuming this product seem unpleasant to you?
 
	1 = Very much 2 = A lot 3 = A little 4 = Very little 5 = Not at all
How likely is it for you to want to purchase this product next week, if it were available?	1 = Very much 2 = A lot 3 = A little 4 = Very little 5 = Not at all
In your opinion, which of these products is most unhealthy?	1 = (image of control beverage) 2 = (image of experimental beverage)
Do you think this product has excess [saturated fat/sugar/sodium]?	1 = Yes 0 = No
Which of these labels would discourage you most from wanting to consume this product?	[answer choices are each of the label types randomly displayed]

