### *Secondary Outcomes*

We hypothesize that the nutrient warning label (compared to other label types) will:

1. Have higher perceived message effectiveness.
2. Be the most discouraging label.

We hypothesize that the nutrient warning label (compared to all other conditions) – and all conditions compared to the control – will:

1. Increase the ability to correctly identify the most unhealthy product when compared with two options.
2. Increase the ability to correctly identify whether a single product contains excess sugar, saturated fat, or sodium.
3. Lower intentions of purchasing a product high in the nutrient of concern in the next week if it were available.

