### **Statistical Methods**

We will use complete case analysis to handle any missing data. We will descriptively report unadjusted means (and standard deviations) and percentages for the primary and secondary outcomes.

We will use a two-sided critical alpha of 0.05 to conduct all statistical tests.

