### **Sensitivity Analyses**

For PME, we will take the average of the 3 items for each product type if  $\alpha > .70$ . For all outcomes assessed between-subjects only, we will then assess whether the outcomes vary by study arm with regression models (linear for continuous outcomes and logistic for dichotomous outcomes).

For outcomes with multiple measurements per-person, we will fit mixed effects linear regression models for continuous outcomes (including PME) and a mixed effects logistic regression model for binary outcomes (including product selection, label selection, identification of healthier products), treating the intercept as random to account for repeated measures.

We will include indicator variables for warning message (between-subjects) and product type (within-subjects), as well as an interaction of warning message and product type. We will use postestimation commands to conduct pairwise comparisons of the predicted means to examine differences by all label types. We will correct for multiple comparisons. To evaluate the most discouraging label, we examine the proportion of participants that selected each warning label as the most discouraging and will conduct z-

tests to explore statistical significance of these differences. To assess whether the effect of the warning label on the primary outcomes differs by education, we will test for an interaction of warning label with low versus high education level (specified as dummy variables) and use a Wald chunk test to determine the joint interaction. We will use postestimation commands to predict means by warning label and education level and conduct pairwise comparisons of the predicted means.

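### Does coding the Likert items from 1 (most) to 5 (least) turn the message-effectiveness and purchase-likelihood results the wrong way round?

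*Combined protocol and SAP*

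**What the plan says.** The table under Screening and Monitoring Evaluations and Measurements prints the same five response options for the three PME items and for the purchase item: "1 = Very much 2 = A lot 3 = A little 4 = Very little 5 = Not at all". All four items are worded towards the construct. The PME items ask about concern, discouragement and unpleasantness, and the purchase item reads "How likely is it for you to want to purchase this product next week, if it were available". Code 1 is therefore the strongest response on each.

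Under Secondary Outcomes in the Statistical Analysis Plan, the nutrient warning is expected to do two things on these measures: "Have higher perceived message effectiveness" and "Lower intentions of purchasing a product high in the nutrient of concern in the next week if it were available".

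On scoring, Sensitivity Analyses says "For PME, we will take the average of the 3 items for each product type if" Cronbach's alpha exceeds .70. It then fits linear models to continuous outcomes, with a random intercept where a person contributes several measurements, and compares predicted means between labels. Statistical Methods adds "We will descriptively report unadjusted means (and standard deviations) and percentages for the primary and secondary outcomes" and sets a two-sided alpha of 0.05 for all tests. No section mentions reverse-scoring, recoding or which end of either scale is favourable.

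**The concern.** Read literally, the PME score is the average of three codes that fall as effectiveness rises, and the purchase score falls as intention rises. An arm answering *A lot* to every PME item would score 2.0 and an arm answering *Very little* would score 4.0, so the weaker label would carry the higher PME mean. A reader who takes the score names at face value would see the opposite of what participants said, on two of the five secondary outcomes.

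Direction matters in this trial. The hypotheses are directional, and the Background says the work is meant to inform the Ministry of Health. A highly significant difference read the wrong way round would favour the wrong label.

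**Working it through.** **The plan's own figure.** The only computed figure is in Sample Size and Power: about 8,000 participants, alpha 0.05, 80% power, f = 0.037, odds ratio 1.14. A four-group one-way ANOVA with noncentral F gives 80.2% power at f = 0.037, and exp(2 × 0.037 × π/√3) = 1.144, so the figure reproduces. It concerns the primary outcomes and does not bear on this point.

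**Inputs.** The codes 1 to 5 come from the measurement table. The three-item average, the reliability threshold and the linear models come from Sensitivity Analyses. The two-sided 0.05 level comes from Statistical Methods. The response shares in step 4 are assumed, because the documents give none.

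**1. Effect on the score.** Reversal replaces x by 6 − x. The mean of the three reversed items is (1/3) Σ(6 − xᵢ) = 6 − x̄. Averaging and then reversing gives the same score as reversing and then averaging, because all three items run the same way.

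**2. Effect on comparisons.** For two arms with means m₁ and m₂, (6 − m₁) − (6 − m₂) = −(m₁ − m₂). Since Var(6 − x) = Var(x), the standard error is unchanged, so t becomes −t and the two-sided p-value is identical. In the mixed model the intercept b₀ becomes 6 − b₀, each label, product and interaction coefficient changes sign, and the variance components stay as they were. Every pairwise contrast keeps its size and p-value, and so does any multiplicity correction applied to those p-values.

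**3. Effect on the reliability rule.** Item variances and covariances are unchanged under 6 − x, so Cronbach's alpha is too. On simulated items it is 0.719 both ways. The rule for forming the average gives the same answer.

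**4. Illustration (assumed shares).**

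| Label | Shares on codes 1–5 | Mean as printed | Mean reversed |
|---|---|---|---|
| More effective | 40/30/15/10/5% | 0.40 + 0.60 + 0.45 + 0.40 + 0.25 = 2.1 | 6 − 2.1 = 3.9 |
| Less effective | 5/10/15/30/40% | 0.05 + 0.20 + 0.45 + 1.20 + 2.00 = 3.9 | 6 − 3.9 = 2.1 |

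The difference is 2.1 − 3.9 = −1.8 as printed and +1.8 reversed. In simulated data with 2,000 per arm, the t statistic goes from −46.3 to +46.3 with the same p-value.

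**5. Are the printed codes meant as final scores?** In the same table, both primary items and the most-unhealthy item are coded 1 or 2 by product image. The outcome lists under Study Objective describe these as choosing the less healthy drink or giving a correct answer, and Sensitivity Analyses models dichotomous outcomes by logistic regression. An indicator has to be built from the 1/2 codes, and no section states that step. The table therefore records response options, and derivation of the named variables is left implicit for the primary outcomes as well. The Likert rows cannot be singled out as finished analysis scores.

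**6. Do the hypotheses conflict with the codes?** They are worded as constructs (more effectiveness, less intention to buy), not as higher or lower numbers. No section says that a larger PME mean indicates a more effective label, and none sets a one-sided test or a numeric cut-off that would depend on orientation.

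**The case for a change.** The strongest case for a change is that the silence falls on just these items. For the image-choice items the plan at least names the event to be counted, so the required indicator is obvious. For PME it gives an explicit rule, the average of three items, with no reversal in it, and a programmer who follows that rule produces a score that runs against its name. For purchase likelihood there is no scoring rule at all. A two-sided p-value does not say which label did better; the sign does, and a policy reader will look at the sign. The remedy would cost one sentence.

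Part of this stands. The score direction is not stated, and a table headed PME that showed raw means without a note would invite misreading. But that the items will be analysed unreversed is inferred from silence; the plan never says so. For the purchase item, even the use of a mean follows only from the general rule for continuous outcomes, since PME is the only such outcome named. The harm also needs analysts to overlook the verbal anchors on their own five-point scale when they score, label and interpret the results. Reversing the codes, or noting beside the results that lower scores mean more of the construct, resolves it equally well. Either can be done at any time without affecting the data or the inference.

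**Conclusion.** No change to the plan is needed. The observation about the codes is accurate, but it amounts to an unstated score direction for two secondary outcomes. Its largest possible effect is on sign and presentation: each mean m becomes 6 − m and each difference changes sign. Effect sizes in absolute terms, two-sided p-values, pairwise findings, the reliability rule and the sample size are all unaffected.

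This rests on three features of the plan: the three PME items run in the same direction, the tests are two-sided, and nothing depends on a numeric cut-off or on combining these items with others scored the opposite way. It also assumes that analysts read the anchors when they build and label the scores, as they must do with the image codes for the primary outcomes. This is a gap that routine scoring fills, and amending the plan would change no result.
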